1.7 SIMULINES PRE-CLINICAL STUDIES BACKGROUND

An important component of Ultherapy® treatment is patient comfort. [REDACTED]

[REDACTED] There are 3 main factors contributing to patient comfort, each of which have been considered when developing the Simulines transducer: 1) spatial (distance), 2) temporal (time) and 3) patient fatigue.

Spatial refers to the proximity of the TCPs to each other and to nerve endings within the tissue. The higher the number of TCPs delivered the more closely packed the TCPs will be in a given area and the more likely that TCPs will be close to or on top of nerve endings. In a face/neck treatment following the conventional guideline, the space between lines is approximately 2-3mm. The clinician advances the transducer this distance between each delivery of a treatment line. [REDACTED]

[REDACTED] As with the Standard transducers, if patient discomfort is experienced the space between the treatment lines may be increased, i.e., the clinician advances the transducer a greater walk distance, and delivery of the recommended number of treatment lines may be completed in multiple passes within an area. Clinicians will be asked to advance the Simulines transducer approximately twice the distance that the Standard transducer is advanced. When delivering a treatment using a Simulines transducer, the same number of treatment lines are delivered, but with only half as many instances of delivering pulses of energy. [REDACTED]

The second factor is the temporal component. It is known from experience with over 500,000 treatments globally, that the more time allowed between pulses of energy the more comfortable the patient is. If a patient is comfortable, a clinician is able to deliver the treatment lines quickly with little time between pulses. If the patient is experiencing discomfort the time between pulses may be increased. This ability to control timing of pulses by the clinician is similar between Standard transducers and Simulines transducers. If a patient is uncomfortable the clinician may pause between each Simulines pulse to increase comfort. This temporal component is also important when looking at the delivery of a single line. At the beginning of delivery of a line of treatment, it is common for a patient to not feel much discomfort; however, patients have experienced a heightened sensation as the last few TCPs in that treatment line are delivered. This has been referred to as “wind up”. Each TCP is delivered in 21-50 milliseconds with up to 23 TCPs per treatment line, and it is theorized that there is a delay in perceiving discomfort. C-fiber nerve conduction velocity is 0.5-20 meters/second which may explain the heightened sensation as the delivery of each treatment line progresses/time passes. [REDACTED]

The third component of discomfort is patient fatigue. It is also known after years of clinical experience with this device that the longer it takes to complete a treatment the more discomfort a patient experiences. It is expected that the Simulines transducer will have a positive impact on patient fatigue, and therefore a positive impact on treatment-related comfort. Delivering two treatment lines at once is expected to shorten treatment time and reduce patient fatigue.

In addition, damage of tissue causes the release of neuropeptides, kinases, substance P, etc. which activate nerve endings. It is expected that local release of these substances around TCPs created by either single or double lines will not be different.

1.7.1 SIMULINES TRANSDUCER OVERVIEW

The Simulines transducers, referred to as DS 4-4.5S and DS 4-3.0S, are capable of delivering two treatment lines simultaneously at the same focal depth.

The energy settings were validated against the conventional treatment in tissue mimicking material, porcine muscle, and in-vivo porcine skin.

The safety of the derived DS 4-4.5S and DS 4-3.0S energy settings was evaluated in a 96 hour porcine survival dosage study by monitoring the animal for evidence of erythema, edema, and contusion on the skin surface after treatment. Each energy setting of each transducer, DS 4-4.5S and DS 4-3.0S, was evaluated by itself and in combination with the other Simulines transducer at the same energy level. The survival data suggested little to no skin surface effects when treating with the derived DS 4-4.5S, and DS 4-3.0S energy settings. Any skin effects resolved within hours which is equivalent to conventional transducers.

Based on this body of data, the DS 4-4.5S transducer, produces TCPs similar in size to the Standard DS 4-4.5 transducer. The DS 4-3.0S transducer produces a line of TCPs that affect a similar amount of tissue compared to the Standard DS 7-3.0 transducer but requires only 20 TCPs versus 23 TCSs with the DS 7-3.0mm transducer.

1.7.2 TRANSDUCER LABORATORY TESTING

Simulines DS 4-4.5 and DS 4-3.0 transducers were built and tested in a number of mediums for evaluation of the amount of coagulated tissue produced by a line. This section summarizes the evaluation performed. Table 1.7.2-1 and 1.7.2-2 describes energy settings used during testing. This study will be carried out using Standard and Simulines transducers set at Energy Level 2 [EL2].

[REDACTED]

[Redacted]

2. STUDY OBJECTIVE AND DESIGN

2.1 STUDY OBJECTIVE

The objective of this study is to demonstrate that the safety and efficacy of Simulines transducers at Energy Level 2 [EL2] is not inferior to treatment with Standard transducers at Energy Level 2 [EL2] in order to limit the energy level of both types of transducers to a maximum of EL2 for lift indications. To fulfill this objective we will be using the same treatment depths and regions treated as those used in the pivotal study that supported the submental/neck clearance, but at EL2 instead of Energy Level 4 [EL4]. Simulines transducers deliver 2 lines of treatment per pulse (push of the button) versus Standard transducers which deliver 1 line of treatment per pulse.

2.2 TYPE AND DESIGN OF STUDY

This study is a prospective, randomized, double blinded multi-center, parallel arm, non-inferiority clinical trial to be conducted at up to eight clinical sites. Up to 260 subjects (a minimum of 20 subjects and a maximum of 45 subjects at each clinical site) will be enrolled and treated if they meet the inclusion/exclusion criteria and provide written informed consent, in a staged study initiation. In an initial stage, 15 subjects will be randomized and treated at one clinical site. Following FDA approval of a safety report, enrollment at all study sites will commence. Investigator or qualified study staff member will assess baseline criteria prior to treatment to confirm eligibility.

Enrolled subjects meeting all entrance criteria and confirmed eligible for study treatment will be randomized into one of two treatment groups. Subjects will be treated using the Ulthera[®] System by the study investigator, sub-investigator or qualified study staff member. Subjects and the study clinician performing efficacy assessments should remain blinded to the assigned treatment group. Standardized images will be taken prior to treatment, following treatment (30 to 60 minutes post-treatment), and during each follow-up visit using Quantificare software, a head positioning device, and a 2D digital imaging system. Quantificare 3D imaging (at up to 3 sites on up to 135 study subjects, these images will be used for marketing purposes only) will also be used to assess volumetric changes. The 3D photograph and volumetric change data will only be used for marketing purposes, not as a support for the primary efficacy analysis. Baseline assessments and pre-treatment images should be obtained within 14 days of the study treatment.

2.3 DURATION OF STUDY

It is expected that recruitment for this study will take 5 months. After the treatment visit, subjects will be followed for a total duration of 365-days. Therefore, the anticipated total duration of the study is approximately 17 months.

3. STUDY PROCEDURES

3.1 SCHEDULE OF ASSESSMENTS AT EACH STUDY VISIT

Table 3.1-1 provides an overview of the subject screening procedure, baseline evaluation, treatment plan, and follow-up requirements.

TABLE 3.1-1: SCHEDULE OF ASSESSMENTS

Evaluation / Procedure	Screening Visit	Baseline Visit ⁺	Treatment Visit ⁺	Telephone Contact Day 3 ± 1D Day 7 ± 2D	Day 90±14 Follow-up	Day 180±21 Follow-up	Day 365±30 Follow-up
Informed Consent	√						
Eligibility Assessment (Inclusion/Exclusion ¹)		√ ⁴					
Demographics and Medical History		√					
Pregnancy Screening [^]		√					√
Skin Examination ²		√	√				
Treatment of Face and Neck			√				
Collection of Treatment Time from System Treatment Log			√				
Subject Assessment of Pain ³			√				
2D images; 3D Images (at applicable site(s))	√	√ ⁴	√ ⁵		√	√ ⁶	√ ⁶
Masked Qualitative Assessments					√	√	√
Jawline Scale		√			√		
Patient Satisfaction Questionnaire					√		
Clinician Global Aesthetic Improvement Scale - CGAIS					√	√	√
Subject Global Aesthetic Improvement Scale - SGAIS					√	√	√
Clinician Blinding Questionnaire							√
Subject Blinding Questionnaire							√
Adverse Event Assessment		*	*	*	*	*	*

+Baseline and Treatment Visits may be separate visits or combined into one visit.

[^] Pregnancy:

- a. If a subject becomes pregnant after the Baseline visit and after study treatment, the subject should continue to be followed.
- b. If a subject becomes pregnant after the Baseline visit but before study treatment, the subject should be exited from the study.

*Complete AE Form when necessary.

NOTES:

1. Baseline Form
2. Baseline Clinical Observations (Pre-Treatment) or Clinical Safety and Adverse Events (Post-Treatment and at Follow-up Intervals).
3. Subject Pain Assessment Scale using a validated Numeric Rating Scale. Pain scores should be obtained following each region treated and for each transducer used. Record the average pain score for the entire region treated.
4. Baseline assessment and pre-treatment photos should be obtained within 14 days of study treatment. Screening photos may be used as Baseline photos
5. Post-treatment images taken 30-60 minutes following Ultherapy® treatment for documentation of immediate post-treatment AEs.
6. Images taken on this visit, but not a primary endpoint for efficacy.

4. SUBJECT SELECTION AND PRE-TREATMENT

The study population will consist of males and females between 30 and 70 years of age who have chosen to participate in this clinical trial as evidenced by execution of the informed consent document.

4.1 PRE-TREATMENT RECRUITING/SCREENING

Subjects who meet the enrollment criteria will be selected by the principal investigator from the study site's patient database and/or who are recruited using IRB approved recruitment materials. Study site personnel will explain the design and purpose of the study to potential study subjects. Subjects interested in participating will visit the study site where informed consent will be obtained.

4.2 INFORMED CONSENT

Written informed consent will be obtained from all subjects before any study-related procedures, including any pre-treatment screening procedures, are performed. Investigators, or qualified study staff member, may discuss the availability of the study and the possibility for entry with a potential subject without first obtaining consent. Informed consent must be obtained and documented prior to initiation of any procedures that are performed solely for the purpose of determining eligibility for research.

Investigators have ethical and legal responsibilities to ensure that the protocol is clearly explained to each subject considered for enrollment in the study. Compliance with this requirement should be documented on a written Informed Consent Form approved by the reviewing IRB. Each Informed Consent Form will include the elements required by FDA regulations in 21 CFR Part 50.

The IRB-approved Informed Consent Form will be signed by the subject and the investigator, sub-investigator, clinical research coordinator, or other qualified study staff member obtaining consent. The subject will be given a copy of the signed Informed Consent Form. The investigator will keep the original on file. A copy will be placed in the subject's chart.

4.3 ELIGIBILITY

4.3.1 INCLUSION CRITERIA

Subjects must meet all of the following criteria for study enrollment:

1. Male or female, age 30 to 70 years.
2. Subject in good health.
3. BMI \leq 30.
4. Skin laxity in the area(s) to be treated as determined by trained physician assessors.
5. Willingness to avoid excessive or prolonged exposure to sunlight, tanning booths, sun lamps, or UV light sources.
6. Willingness to apply study provided sunscreen (Neocutis Micro-Day Rejuvenating Cream) daily until study exit to help limit sun exposure.
7. Willingness to avoid or periodically stop use of Sunless Tanners (washout period of two weeks prior to each study visit is required).
8. Understands and accepts the obligation not to undergo any other procedures in the areas to be treated through the follow-up period.
9. Willingness to avoid non-emergent dental procedures in the 3 weeks prior/post treatment.

10. Willingness and ability to comply with protocol requirements, including returning for follow-up visits and abstaining from exclusionary procedures for the duration of the study.
11. Subjects of childbearing potential must have a negative urine pregnancy test result and must not be lactating at the Screening Visit and be willing and able to use an acceptable method of birth control (e.g. barrier methods used with a spermicidal agent, hormonal methods, IUD, surgical sterilization, abstinence) during the study. Women will not be considered of childbearing potential if one of the following conditions is documented on the medical history:
 - a. Postmenopausal for at least 12 months prior to study;
 - b. Without a uterus and/or both ovaries; or
 - c. Bilateral tubal ligation at least six months prior to study enrollment.
12. Absence of physical or psychological conditions unacceptable to the investigator.
13. Willingness to refrain from use of aspirin, Ibuprofen, Naproxen or any other NSAID prior to each study treatment and chronic use during the entire post-treatment study period. Washout period, if chronic user, for 4 weeks prior to the study treatment. After study treatment is completed, limited acute NSAID use, i.e., a maximum of 2-3 doses in any 2 week period, is allowed if needed.
14. Willingness and ability to provide written consent for study-required photography and adherence to photography procedures (i.e., removal of jewelry and makeup).
15. Willingness and ability to provide written informed consent and HIPAA authorization prior to performance of any study-related procedure.

4.3.2 EXCLUSION CRITERIA

Subjects will be excluded if they meet any of the following criteria:

1. Presence of an active systemic or local skin disease that may affect wound healing.
2. History of Bell's Palsy.
3. History of chronic or frequently recurring episodic (recurrent episode in past 12 months) autoimmune diseases such as Multiple Sclerosis, Crohn's Disease, Psoriasis, Myasthenia Gravis, Lambert-Eaton Syndrome that has required immune suppressant therapy (such as biologic drug or corticosteroid treatment).
4. Palpable thyroid lesion, lymphadenopathy, or other pathological changes within the treatment area.
5. History of skin cancer in the areas to be treated, basal cell nevus syndrome, or jaw cysts
6. Known allergy or sensitivity to Ibuprofen.
7. Severe solar elastosis.
8. BMI > 30.
9. Significant changes in weight (e.g. more than 5 pounds) over the past 6 months or anticipated significant changes in weight or diet over the course of the study.
10. Pregnant within the past year.
11. Excessive subcutaneous fat in the area(s) to be treated as determined by trained physician assessors.
12. Excessive skin laxity in the area(s) to be treated.
13. Significant scarring in the area(s) to be treated that would interfere with assessing results.
14. Open wounds or lesions in the area(s) to be treated.
15. Severe or cystic acne on the area(s) to be treated.
16. Active implants (e.g., pacemakers or defibrillators), or metallic implants in the treatment areas (dental implants not included).
17. Inability to understand the protocol or to give informed consent.
18. Microdermabrasion, or prescription level glycolic acid treatment to the treatment area(s) within two weeks prior to study participation or during the study.
19. Marked asymmetry, ptosis, excessive dermatochalasis, deep dermal scarring, or thick sebaceous skin in the area(s) to be treated.

20. History of chronic drug or alcohol abuse.
21. Concurrent therapy that, in the investigator's opinion, would interfere with the evaluation of the safety or efficacy of the study device.
22. Subjects who anticipate the need for surgery or overnight hospitalization during the study.
23. Subjects who, in the investigator's opinion, have a history of poor cooperation, noncompliance with medical treatment, or unreliability.
24. Concurrent enrollment in any study involving the use of investigational devices or drugs.
25. Current smoker or history of smoking in the last five years.
26. Current user of any nicotine-containing products, e.g., e-cigarettes, Nicorette gum, nicotine patches, etc.
27. History of the following cosmetic treatments in the area(s) to be treated:
 - a. Any energy based device (RF, MFU, etc.) procedure for skin tightening within the past year;
 - b. Injectable filler of any type within the past:
 - i. 12 months for Hyaluronic acid fillers (e.g. Restylane)
 - ii. 12 months for Ca Hydroxylapatite fillers (e.g. Radiesse)
 - iii. 24 months for Long Lasting Hyaluronic acid (e.g. Voluma) and Poly-L-Lactic acid fillers (e.g. Sculptra)
 - iv. Ever for permanent fillers (e.g. Silicone, ArteFill)
 - c. Neurotoxins within the past six months (neuromodulators are allowed in the glabella and forehead, not allowed in the temples, crow's feet or anywhere below the lateral canthus);
 - d. Fractional and fully ablative resurfacing laser treatment within the past two years;
 - e. Nonablative, rejuvenative laser or light treatment within the past six months;
 - f. Surgical dermabrasion or deep facial peels within the past two years;
 - g. Facelifts, neck surgery (e.g. thyroid, neck lifts, neck liposuction, etc.) within the past two years
 - h. Micro needling within the past year;
 - i. Kybella, Coolsculpting, or Mesotherapy within the past two years; or
 - j. Any history of contour threads.
28. History (in the prior year) or current use of the following prescription medications:
 - a. Accutane or other systemic retinoids within the past six months;
 - b. Initiation of topical retinoids within the past 6 months or throughout the course of the study;
 - c. Antiplatelet agents/Anticoagulants (Coumadin, Heparin, Plavix);
 - d. Systemic steroids including prednisone;
29. Dermal regulators of collagen;
30. Initiation of bioidentical hormones or HGH within the past 6 months or throughout the course of the study; or
31. Psychiatric drugs that in the investigators opinion would impair the subject from understanding the protocol requirements or understanding and signing the informed consent.

After subjects have provided informed consent and met the inclusion/exclusion criteria, the study procedures described in the following section will be performed. Subjects can be enrolled in the study and treated according to this protocol on the same day.

4.4 SCREEN FAILURES

A screen failure subject is one from whom informed consent is obtained and is documented in writing (i.e., subject signs an Informed Consent Form), but who does not receive a study treatment because of failure to meet all of the eligibility criteria. Screen failure subjects will be included in the total number of subjects enrolled (i.e., all subjects consented), but not counted towards the total subjects treated.

4.5 SUBJECT RANDOMIZATION AND TREATMENT GROUP ASSIGNMENT

At the Treatment visit, only qualified study subjects (i.e., signed the IRB-approved consent form and confirmed eligible) will be randomly assigned according to a computer-generated 1:1 randomization to receive Ultherapy® treatment using either the Simulines or Standard transducers.

Randomizations will be stratified by site and will use randomly selected blocks of size 4 and 6 and will be generated by an electronic database in a reproducible fashion and will be provided to the site by electronic data capture the point that randomization occurs.

Enrolled subjects will be randomized to one of two treatment groups. Subjects and the study clinician performing efficacy assessments should remain blinded to the assigned treatment group. All randomized subjects will receive a single, dual depth lower face and neck Ultherapy® treatment. Group A will receive treatment with Standard transducers at EL2. The number of treatment lines in each region currently requiring an odd number of lines will be rounded up to an even number for equivalency between Standard and Simulines (e.g. if 15 lines are required in a region on the Standard transducer treatment map then this will be rounded up to 16 lines to match the 16 lines required on the Simulines map). Group B will receive treatment with Simulines transducers at EL2.

Subjects randomized to Group A will receive an Ultherapy® treatment to the lower face and neck with a total minimum pulse count of 672 pulses (+5%) at the 4.5mm and 3.0mm depths using Standard transducers. Energy levels for each transducer will be set to EL2:

- DS 4-4.5 at 0.9J with pitch of 1.5mm and 17 TCP's per line
- DS 7-3.0 at 0.30J with pitch of 1.1mm and 23 TCP's per line

Subjects randomized to Group B will receive a comparable treatment with a total minimum pulse count of 336 pulses (+5%) using the Simulines transducers at the 4.5mm and 3.0mm. Energy levels for each transducer will be set to EL2:

The assigned treatment group should be documented on the appropriate study-specific data form and study log.

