4.6 STUDY IMAGES

At all sites, the images in the study will be obtained using the 2D Quantificare digital photo system and software for image collection, storage, and analysis. To ensure consistent, reproducible study photos from baseline photographs to the follow-up photographs, Quantificare photography guidelines and procedures must be followed, see **Attachment H**. Site personnel will be trained on these guidelines at the Investigator Meeting. The following photographs should be obtained at each study visit, for each imaging system used:

- Screening/Baseline 2D photographs, capturing 5 views: Frontal View; Right and Left Lateral (90°); Right and Left Oblique (45°);
- Immediate Post-treatment Standard 2D photographs, capturing 3 views: Frontal View; Right and Left Lateral (90°).
- 90 Day Follow-Up Standard 2D photographs, capturing 5 views: Frontal View; Right and Left Lateral (90°); Right and Left Oblique (45°);

- Day 180 Follow-Up Standard 2D photographs, capturing 5 views: Frontal View; Right and Left Lateral (90°); Right and Left Oblique (45°);
- Day 365 Follow-Up Standard 2D photographs, capturing 5 views: Frontal View; Right and Left Lateral (90°); Right and Left Oblique (45°);

Subjects' Screening/Baseline images are considered the pre-treatment comparator images. Screening/Baseline images may be taken within 14 days prior to study treatment. ***Subject photos must be reviewed prior to study treatment to ensure proper subject selection and photographic quality.***

At up to 3 sites (in up to 135 subjects), additional images will be obtained using a 3D Quantificare system, see **Attachment I** (these images will be used only for marketing purposes). To ensure consistent, reproducible study photos from baseline to follow-up, Quantificare's photography guidelines and procedures must be followed, see **Attachment H**. Site personnel will be trained on these guidelines on an individual basis by Quantificare prior to study enrollment.

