5.1.4 TREATMENT

All study treatments will be performed by the investigator, sub-investigator, or qualified study staff member (i.e., study treatment clinician as designated by the principal investigator.) The study clinician performing efficacy assessments should remain blinded to the assigned treatment group, and therefore may not perform study treatments.

Ultrasound gel will be applied to the transducer, which will then be placed on the targeted skin surface, and ultrasound image will be obtained. Each area of the proposed treatment will be imaged first with the ultrasound device to ensure coupling between the transducer and skin. During the treatment procedure, the study treatment clinician will place multiple Ultherapy[®] treatment lines close to each other in the selected area, with each treatment line requiring about 3 seconds. When using the Simulines transducer the distance the transducer should be advanced between delivery of treatment lines should be doubled as 2 lines of treatment are laid down simultaneously. It is also recommended that at least 2 to 3 passes are used to deliver all lines in each section to allow for tissue cooling between passes of energy delivery. Treatment lines can be a maximum length of 25mm and will produce a series of thermal coagulative points.

Treatment lines to the area highlighted in (Figure 5.1.3-1) above will be administered as specified by Treatment Group. Energy joules delivered for study treatments will be 0.9J joules [EL2] for the Standard 4-4.5mm transducer and 0.30J [EL2] for the Standard 7-3.0mm transducer. [REDACTED]

All study treatments will begin with the 4.5mm depth. The entire 4.5mm depth treatment will be completed prior to continuing to the 3.0mm depth treatment. Treatment will be delivered in a lined pattern. The subject will be monitored during the treatment.

The time each treatment begins and ends will be captured and recorded on the source documents.

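### Nothing stops a person who knows the earlier allocations at a site from selecting or clearing the next subject, and site-level blocks of disclosed size make the next arm partly predictable

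*Combined protocol and SAP*

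**What the plan says.** **Allocation.** Section 4.5 specifies a "computer-generated 1:1 randomization" and adds: "Randomizations will be stratified by site and will use randomly selected blocks of size 4 and 6". Only subjects who have consented and been confirmed eligible are randomised, at the treatment visit. The assignment "will be provided to the site by electronic data capture the point that randomization occurs" and is then recorded on a data form and study log. No restriction on who may read the log is stated.

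**Who selects, clears and treats.**
- Section 4.1: subjects who meet the criteria "will be selected by the principal investigator from the study" site's database, or are recruited with approved materials.
- Section 2.2: "Investigator or qualified study staff member will assess baseline criteria prior to treatment to confirm eligibility". Treatment is given "by the study investigator, sub-investigator or qualified study staff member".
- Section 5.1.4: the clinician who assesses efficacy "should remain blinded to the assigned treatment group, and therefore may not perform study treatments". This is the only separation of roles stated.

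**Judgement criteria.** Sections 4.3.1 and 4.3.2 require laxity that is present but not excessive, and no excessive subcutaneous fat. Trained physician assessors are named for laxity (4.3.1), for excessive fat (4.3.2) and, in the synopsis, for excessive laxity. They are not said to be separate from treating staff or unaware of earlier allocations.

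**Photographs.** Section 4.6: "Subject photos must be reviewed prior to study treatment to ensure proper subject selection and photographic quality".

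**The concern.** Whoever treats knows the arm: the transducers differ and the minimum pulse counts are 672 against 336 (section 4.5). If that person, or anyone who reads the log, also decides whom to put forward or whether borderline laxity or fat passes, their expectation of the next arm can influence who enters it.

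Concealing the current allocation does not prevent this. In a blocked list within a site, past allocations carry information about the next one. The blinded measurement of submental area (section 6.4.3.1) protects against biased measurement, but not against differences in who was admitted.

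The stake is the primary comparison. Study success rests on one unadjusted, unpooled Z-test of responder proportions against a 15-point margin at one-sided 0.05 (sections 6.2 and 6.4.3.1). A selection effect of a few points towards Simulines would favour a non-inferiority conclusion. The same effect in the other direction would cost power.

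**Working it through.** **1. The plan's own figures reproduce.** Inputs from section 6.4.3.1: 73% response in both arms, margin 15 points, one-sided alpha 0.05, power 80%, unpooled Z.

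n per arm = (1.645 + 0.842)² × 2 × 0.73 × 0.27 / 0.15² = 108.3, so 109. In total 218, and 218 / 0.84 = 259.5, so 260. The sample size is not in question.

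**2. Predictability in closed form.** Take the simple rule of guessing the arm that is behind and tossing a coin when the arms are level. In a balanced block of 2m, the expected number of correct guesses is m + 2^(2m−1)/C(2m, m) − 1/2.

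- Block of 4: 2 + 8/6 − 0.5 = 2.833, or 70.8% (17/24).
- Block of 6: 3 + 32/20 − 0.5 = 4.1, or 68.3%.
- Sizes equally likely (an assumption; section 4.5 says only that they are randomly selected): (2.833 + 4.1) / 10 = 69.3%.

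This rule uses no knowledge of the block sizes. Every block ends level, so the running imbalance at the site is the imbalance within the current block.

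**3. Predictability by simulation at real site sizes.** Section 2.2 sets 20 to 45 subjects per site, so the last block may be cut short. With 6,000 sequences at each size and a guesser who knows all earlier allocations and both block sizes:

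| Site size | Best guess correct | Arm-behind rule correct | Next arm certain | Next arm at least 75% probable |
|---|---|---|---|---|
| 20 | 68.5% | 68.5% | 5.9% | 45.6% |
| 32 | 68.8% | 68.8% | 5.7% | 47.4% |
| 45 | 68.7% | 68.7% | 5.6% | 47.5% |

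The chance level is 50%. Certainty at 5.7% is about 15 of 260 subjects (0.057 × 260 = 14.8). Knowing the sizes supplies these certain cases but leaves the hit rate essentially unchanged.

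**4. From guess to bias.** Let a guess of Simulines raise the admitted subject's expected response by η, and a guess of Standard lower it by η. With 68.6% of guesses correct,

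bias = 2η × (2 × 0.686 − 1) = 0.744η.

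- η = 2 points: 1.5 points.
- η = 5 points: 3.7 points.

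The documents give no value for η. Both are assumptions, and the formula has every guess acted on in the same direction.

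**5. Effect on false non-inferiority.** At the null boundary (73% v 58%, 109 per arm), SE = √[(0.73 × 0.27 + 0.58 × 0.42)/109] = 0.0636. The normal approximation is 1 − Φ(1.645 − bias/SE).

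| η | Bias, points | Normal approximation | Simulated trials |
|---|---|---|---|
| 0 | 0 | 5.0% | 4.6% |
| 2 | 1.5 | 7.9% | 7.5% |
| 5 | 3.7 | 14.5% | 14.4% |

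The simulation used 6,000 trials with 8 sites, 260 randomised and 218 evaluable. A separate simulation gave 5.4%, 8.0% and 13.8%.

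**6. The opposite direction.** At 73% in both arms, SE = √(2 × 0.73 × 0.27/109) = 0.0601. Power is Φ((0.15 − bias)/SE − 1.645): 80.2% with no bias, 72.6% if 1.5 points are lost, and 59.1% if 3.7 points are lost. The same caveats apply.

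**The case against.** **The current allocation is concealed, and block size varies.** This is correct. Eligibility is confirmed before randomisation and the assignment is released electronically at that moment. It would be wrong to call this an open-selection comparison. What remains is prediction from earlier allocations, which is probabilistic and rarely certain.

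**A reader might infer from section 4.6 that the photo review can follow allocation**, because it is tied to treatment. The rest of the text does not support this. The synopsis treatment outline takes screening photographs to confirm eligibility, section 4.5 randomises only subjects already confirmed eligible, and section 5 lists photography before randomisation. The gap is only that no electronic lock enforces the order.

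**The principal investigator may be blinded.** Section 5.3 assigns the CGAIS to the principal investigator or a delegate, and 5.1.4 bars the efficacy assessor from treating. A principal investigator who does the CGAIS must therefore be blinded and cannot treat. This stands for those sites, but delegation is allowed, so it guarantees nothing. Knowing every earlier allocation also requires that one person treats everyone at the site or reads the log. The documents neither state nor prevent that.

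**Printing the block sizes does little.** This also stands, as steps 2 and 3 show.

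**Planned outputs might reveal steering.** In part they might. Section 6.4.1 tabulates demographics, BMI and medical history by arm, and response by arm and site. Baseline submental area and the jawline scale are rated blind. A reader might infer that no planned analysis could detect the problem, but that goes too far. The primary test, however, adjusts for none of these.

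**No evidence of motive or skill.** The documents state no investigator preference, and nothing shows that clinicians can predict a 20 mm² response. This is why the error rates above are upper illustrations, not expectations.

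**Conclusion.** The concern holds as a design vulnerability. The plan discloses block sizes to sites, and it leaves an unblinded treater or a log reader free to select subjects and judge subjective criteria. With full knowledge of earlier allocations at a site, the next arm can be guessed about 69% of the time and is certain for about 6% of subjects. Site-level blocking accounts for most of this.

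The predictability figures assume that the two block sizes are equally likely. The consequences (a shift of 1.5 or 3.7 points, with false non-inferiority rising from about 5% to about 7.5% or 14%) rest further on an assumed 2- or 5-point effect, on every guess being acted on, and on a consistent preference for Simulines. The documents support none of these three. A reader might infer that the primary result will be biased towards non-inferiority. The text shows only that the opportunity exists, and the direction could be either.

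This is a low-cost improvement worth making. It is no reason to doubt the sample size or the choice of test.

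**What to change.** 1. **Section 4.5:** delete the two block sizes and hold them in a restricted randomisation specification that sites do not see. On its own this removes only the certain cases.

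2. **Sections 2.2, 4.1 and 4.5:** require that final eligibility, including the photo review, is recorded and locked in the electronic data capture system before the allocation is released. The person who records it should be a qualified assessor who does not treat and has no access to the study log or to earlier allocations. The existing blinded clinician can do this where qualified as a trained physician assessor. Section 5.3 allows a delegated staff member to do the CGAIS, so some sites may need to name another assessor.

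This reduces the risk without fully removing it: choosing candidates from the site's database and timing appointments can still be influenced by someone who knows past allocations.

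**Cost:** protocol wording, one lock in the data capture system, access control on the study log, and a small scheduling burden. The sample size stays at 109 evaluable per arm and 260 randomised.
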